#### 8.2.5.2 Data Review

The process starts with the Statistician writing a Data Review Meeting (DRM) plan and based upon this approved plan, then a DRM will occur prior to database lock. The process ends with the approval of a formal meeting report which describes the decisions made at the data review meeting.

The SAP will be reviewed after the DRM and may be updated if deemed applicable. Details for the DRM will be provided in DRM plan that will cross-reference to the SAP.

#### 8.2.5.3 Multiple Comparisons/Multiplicity

No account for multiple comparisons or multiple testing is performed, as a hierarchical strategy is applied for the primary efficacy endpoint as detailed in section 8.2.2.

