## 8. Analysis Methods

### 8.1 General Methods

Post-Text TLFs are provided in collated electronic PDF files.

For continuous variables, the mean, standard deviation, minimum, median and maximum are presented, together with the total number of observations and the number of missing and non-missing values. Unless otherwise specified, minimum and maximum values are reported to the same number of decimal places as the recorded measurements; mean and median are reported to one more decimal place and standard deviation one additional decimal place more than the mean.

For categorical variables, absolute and relative frequencies are reported. Relative frequencies are based on all observations and reported as percentages to one decimal place. Unless otherwise specified, percentages are based on the number of subjects with data and are not calculated for missing categories.

Adverse events are reported on a per-subject basis, i.e. if a subject reported several events coded to the same coding term the subject is counted only once at the respective level of display. The percentages are calculated using the number of subjects in the population Analysis Set as the denominator.

All hypotheses are tested at a 5% level of significance using a two-sided test unless otherwise specified.

P-values are rounded to three decimal places. If a p-value is less than 0.001 it is reported as "<0.001." If a p-value is greater than 0.999 it is reported as ">0.999.

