#### 8.2.1 Hypothesis and Testing Strategy

The primary and secondary efficacy endpoint analyses aim to demonstrate that there is a difference between baseline and post-baseline in the variable of interest for each endpoint. More formally, the following hypothesis will be tested:

$H_0$ : There is no difference between baseline and post-baseline (Days 7, 14 and 21) in the endpoint of interest.

$H_1$ : There is a difference between baseline and post-baseline (Days 7, 14 and 21) in the endpoint of interest.

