#### 8.2.2 Primary Analysis

The primary efficacy endpoint is the average MVPA at Days 7, 14 and 21 as detailed in section 7.4.7.1.

The primary analysis will follow a hierarchical approach as follows:

1. A Mixed Model with Repeated Measures (MMRM) is used to analyse the change from baseline in MVPA average minutes as the response variable with baseline as a fixed effect. Subjects will be included as a random effect, and timepoint will be treated as a

repeated measure within each subject (with compound symmetry structure between visits). If the parameter for the intercept is found to be statistically significant (p-value < 0.05), then the second model below will be used.

2. A Mixed Model with Repeated Measures (MMRM) is used to analyse the change from baseline in MVPA average minutes as the response variable with baseline and timepoint (with unstructured covariance structure between visits) as fixed effects. Adjusted means for each timepoint will be presented along with p-values and 95% confidence intervals (CIs) for the mean change from baseline in MVPA.

Other than the global test for an overall change from baseline (i.e., intercept), there will be no other adjustment for multiplicity. If data are found to be non-normal, the Friedman Test will be used. If the Friedman test is found to be significant then Wilcoxon Signed Rank Pairwise Tests are used for each week comparison.

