### 8.2.3 Secondary Analysis

The following secondary endpoints are analysed in the manner as described for the primary endpoint described in section 8.2.2:

- Change from baseline on Days 7, 14, and 21 in Daily Average number of steps taken.
- Change from baseline on Days 7, 14, and 21 in Ratio of sedentary/non-sedentary time.
- Change from baseline on Days 7, 14, and 21 in Gait, assessed through speed and step irregularity (measured via cadence and gait speed).
- Change from baseline on Days 7, 14, and 21 in Indices of morning stiffness (assessed through levels of mobility 30- and 60-mins post-wake).
- Change from baseline in self-reported pain intensity, assessed through Numeric Rating Scale (NRS) on Days 7, 14 and 21.
- Change from baseline in WOMAC Physical Function subscale on Days 7, 14, and 21.
- Change from baseline in the WOMAC subscales, Pain (composite) and Stiffness (composite) on Days 7, 14, and 21.
- Change from baseline in the WOMAC Global Score on Days 7, 14, and 21.

The secondary endpoint, study subjects' perceived ability to exercise more regularly, assessed using the WOMAC Physical Function subscale on Days 7, 14, and 21, will be analysed by exploring the correlation between WOMAC Physical Function subscale on Days 7, 14, and 21 and the average MVPA as detailed in section 7.4.7.1 (primary endpoint variable) graphically, by means of Spearman rank correlation.

The following secondary endpoints are analysed by descriptive statistics with no formal statistical hypothesis testing performed:

- MVPA on each day of the study (Baseline to final treatment day 21).
- Change from baseline in Karolinska Sleepiness Scale on Days 7, 14, and 21.
- Change from baseline in Health-related quality of life, EQ-5D-5L, on Days 7, 14, and 21.

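### SAP 8.2.5.3 waives multiplicity adjustment because of a hierarchy that works inside one endpoint only; 11 secondary variables are tested at 5% each, with no link to the primary result and no nominal label

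*SAP*

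**What the plan says.** SAP 8.2.5.3 reads: "No account for multiple comparisons or multiple testing is performed, as a hierarchical strategy is applied for the primary efficacy endpoint". The strategy it points to is in SAP 8.2.2. Step 1 is a repeated-measures model of change from baseline in average MVPA, with baseline as a fixed effect and compound symmetry between visits. "If the parameter for the intercept is found to be statistically significant (p-value < 0.05), then the second model below will be used". Step 2 adds timepoint and gives an adjusted mean, confidence interval and p-value for each of the three timepoints. The section closes: "Other than the global test for an overall change from baseline (i.e., intercept), there will be no other adjustment for multiplicity". Protocol 13.3.1 says the same.

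For the secondaries, SAP 8.2.3 says: "The following secondary endpoints are analysed in the manner as described for the primary endpoint described in section 8.2.2", and eight bullets follow. SAP 8.1 sets the level: "All hypotheses are tested at a 5% level of significance using a two-sided test unless otherwise specified". SAP 8.2.1 states the purpose of both tiers: "The primary and secondary efficacy endpoint analyses aim to demonstrate that there is a difference between baseline and post-baseline".

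SAP 8.2.3 treats the remaining secondaries differently. Daily MVPA, the Karolinska scale and EQ-5D-5L are descriptive without hypothesis tests, and perceived ability to exercise is handled as a correlation.

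**The concern.** The reason given for making no adjustment does not reach the tests it leaves unadjusted. A hierarchy protects several endpoints only if it links them, so that a later test is read only after an earlier one has succeeded. The one in 8.2.2 links an intercept to timepoints of the same variable. Repeating it per secondary variable gives each its own 5% first step and controls nothing across variables.

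If MVPA showed no change, nothing in the plan would stop a significant result for steps, gait speed or a WOMAC subscale from being reported as a demonstrated effect. SAP 8.2.1 would support that reading. With 11 separate chances, one such result by chance alone is not unlikely.

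**Working it through.** **1. Count of tested secondary variables (SAP 8.2.3, with derivations in 7.4.7.2).** Steps 1; sedentary ratio 1; gait 2 (cadence and gait speed, derived separately); morning stiffness 2 (30 and 60 minutes, derived separately); NRS 1; WOMAC function 1; WOMAC pain and stiffness 2; WOMAC global 1. Total: 1 + 1 + 2 + 2 + 1 + 1 + 2 + 1 = 11 first-step tests. With three timepoints each, up to 11 × 3 = 33 further p-values.

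**2. Links between tests.** Within a variable, step 2 depends on step 1. Between the primary and any secondary, and among secondaries, SAP 8.2.2 and 8.2.3 give no order, no split of alpha and no condition.

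**3. Familywise error if nothing changes.** The documents state no such figure, so there is none to reproduce. Inputs: 11 tests (step 1 above) and alpha 0.05 two-sided (SAP 8.1). Correlations are not given and are assumed equal for all pairs.
- Independent: 1 − 0.95^11 = 0.431. Expected number of false positives: 11 × 0.05 = 0.55.
- Simulated equicorrelated normal statistics (400,000 draws):

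| Common correlation | 0 | 0.3 | 0.5 | 0.7 | 0.9 |
|---|---|---|---|---|---|
| At least one false positive | 43% | 37% | 30% | 22% | 13% |

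For jointly normal two-sided statistics, independence gives the upper bound. The true figure lies below it, because WOMAC global is the sum of the three tested subscales (SAP 7.4.7.2) and the 30-minute window lies inside the 60-minute one.

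For the six tracker variables alone: 1 − 0.95^6 = 26% if independent, 21% at correlation 0.5 and 11% at 0.9.

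**4. Does each first-step test have a 5% error?** Not as 8.2.2 is written. The model is change = a + b × baseline + error, and no centring is stated, so a is the expected change at a baseline of zero. With no mean change, 0 = a + b × (mean baseline), so a = −b × (mean baseline). With equal variances and between-period correlation ρ, b = ρ − 1 and a = (1 − ρ) × (mean baseline). For ρ from 0.5 to 0.9 that is 0.5 to 0.1 of the baseline mean, although nothing has changed.

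Simulation with n = 147, three post-baseline weeks, normal data and no mean change (assumed baseline coefficient of variation 0.5 to 1.0, ρ 0.5 to 0.9): the uncentred intercept is significant in about 68% to 100% of trials. With baseline centred at its sample mean the figure is about 6% to 13%. The figures in step 3 are therefore conditional on a repaired first step.

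**5. Power cost of formal adjustment.** Plan inputs (SAP 3.2.1): effect size 0.25, 80% power, two-sided 0.05, Wilcoxon signed rank, 147 completers. Noncentral-t power on N × ARE, where ARE is the efficiency relative to the t test, at the minimum ARE of 0.864 gives N = 148, and 79.8% power at 147. The plan's figure is reproduced.

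Bonferroni over 11: 0.05/11 = 0.00455, which is also Holm's first step. Power per variable at N = 147 falls from 79.8% to 47% (ARE 0.864), or from 84% to 53% (ARE 3/π).

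**The case against.** The lack of adjustment is disclosed and consistent. SAP 8.2.2 and protocol 13.3.1 both say that nothing beyond the global test is adjusted, and 8.2.5.3 names its hierarchy as belonging to the primary. A reader might infer that the SAP claims protection for the secondaries; it does not say so. The defect is a reason that does not cover the tests concerned, combined with the purpose stated in 8.2.1. That part stands.

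This is a Phase IV, open-label, single-arm study, and unadjusted secondary tests are acceptable there if labelled nominal. That is right, and it is why the label is enough as a fix. But the label is missing, and 8.2.3 sets these 11 apart from the secondaries that it declares free of formal testing.

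Pain and function may truly improve; protocol 2.2 cites established effects. A rate that assumes no change anywhere then overstates the risk for those variables. The six tracker variables alone still give 11% to 26%.

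A reader might also infer that the sponsor intends to claim secondary results. No passage states a claim or a regulatory use for any of them.

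**Conclusion.** The point holds. SAP 8.2.5.3 justifies the absence of adjustment by a device that operates within one endpoint, while 11 secondary variables are formally tested at 5%, with no link to the primary result and no nominal label. The size is about 13% to 43% for at least one false-positive secondary first step. This assumes no true change, a genuine 5% error per test and a common correlation between 0.9 and 0.

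Three stronger readings are not supported:
- That 43% is the trial's error rate. It requires independence, and the variables overlap by construction.
- That Holm over 11 variables is required. It is one option, with a real cost in power.
- That the primary first step is sound and can be left alone. As 8.2.2 is worded, its intercept is not the mean change, so making secondaries conditional on it would protect nothing until it is repaired.

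**What to change.** **SAP 8.2.5.3:** replace the sentence with a statement that only the primary global test of mean change in MVPA is confirmatory. All secondary p-values are unadjusted and nominal, and cannot support a claim of a demonstrated effect, whatever the primary result.

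**SAP 8.2.1:** limit the aim of demonstrating a difference to the primary, and describe the secondary analyses as estimation with nominal p-values.

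**SAP 8.2.2:** make the first step test the mean change, for example by centring baseline at its mean. The centred test still ran at about 6% to 13% in the simulation, because the model treats the observed baseline mean as fixed. Omitting the covariate from step 1 makes the intercept the mean change itself; protocol 13.3.1 lists no baseline covariate. The choice should be stated.

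**Alternative:** if confirmatory secondary claims are wanted, prespecify a fixed sequence or a Holm procedure over the 11 first-step tests, conditional on the repaired primary test. Holm's first step leaves about 47% to 53% power per variable at effect size 0.25 and N = 147. A fixed sequence keeps 5% for each test reached but depends on the order, which must be set before results are seen.

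**Cost:** wording, plus one model specification in 8.2.2. There is no change to data, sample size or conduct. The downside is that some nominally significant secondary results cannot be claimed.

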## 9. Interim analyses

No interim analysis is planned for this study.

## 10. Overview of Tables, Listings and Figures

Below is a list is given per topic with variables and populations used in tables. For the content, titles and layout of the full set of tables see the table shells in the appendix.

### 10.1 Disposition of Subjects

Table CCI summarizes the disposition of subjects in the Total Set by treatment and overall. This includes a summary of the number (n) and percentage (%) of: subjects screened; subjects who are screen failures; subjects who are enrolled; subjects who completed the study; subjects

who discontinued the study and the primary reason for discontinuation. Percentages are based on the number of subjects enrolled, percentages are not shown for the number of subjects screened or the number of screening failures.

The number of subjects who attended scheduled visits in clinic and eDiary is summarized in Table CCI (Visit Attendance) by absolute counts (n) and percentages (%), by treatment and overall, for the Enrolled Population.

Listing CCI presents reason for screening failures for all screen failure subjects in the Total Set.

Listing CCI presents disposition data, including informed consent dates, completion status and the primary reason for study discontinuation, for the Total Set.

## 10.2 Protocol Deviations

Listing CCI presents all major protocol deviations for the Enrolled Population.

### 10.2.1 Inclusion and Exclusion Criteria

The eligibility of all subjects for entry into the study is assessed at the screening visit by the Inclusion and Exclusion criteria ('Subject Eligibility: Inclusion/Exclusion Criteria eCRF page).

Listing CCI presents all subjects who failed to meet all of the inclusion and Listing CCI presents all subjects who met any exclusion criteria, along with all their inclusion and exclusion responses, for the Total Set.

## 10.3 Data Sets Analysed

The number of subjects in each Analysis Set defined in Section 6.1 is summarized by absolute counts (n) and percentages (%), by treatment and overall, for the Enrolled Population in Table CCI.

Listing CCI presents the inclusion into each Subject Analysis Set defined in 'Section 6.1', including the primary reason for exclusion from the SAF and mITT, for the Enrolled Population.

## 10.4 Demographic and Other Baseline Characteristics

### 10.4.1 Demographic Characteristics

Descriptive statistics [number of subjects (n), mean, SD, median, minimum and maximum and percentage (%) of subjects] will be presented for demographic characteristics, by treatment and overall. These variables include age (years), sex, race, and ethnicity and will be presented for the Enrolled Population in Table CCI. Percentages are based on the number of subjects with data.

Table CCI summarizes demographic characteristics for the Enrolled Population for US only subjects.

Table CCI summarizes demographic characteristics for the Enrolled Population for EU (Poland) only subjects.

Listing CCI presents all demographic data for the Enrolled Population.

### 10.4.2 Medical History

Listing CCI presents all medical history data for the Enrolled Population.

Listing CCI presents knee osteoarthritis diagnosis data for the Enrolled Population.

#### 10.4.3 Prior and Concomitant Medications

Listing **CCI** presents all prior and concomitant medication data for the Enrolled Population.

Listing **CCI** presents all concomitant procedure data for the Enrolled Population.

#### 10.4.4 Visual Analogue Scale

Listing **CCI** presents all VAS data for the Total Set.

### 10.5 Study Medication

#### 10.5.1 Measurements of Treatment Exposure and Compliance

Treatment exposure and compliance data, including collected and derived, are summarized by summary statistics, by treatment and overall, for the SAF in Table **CCI**

Listing **CCI** presents all treatment exposure and compliance data for the SAF.

Listing **CCI** presents all device accountability data for the SAF.

Listing **CCI** presents all medical product accountability data for the SAF.

Listing **CCI** presents all study product use data for the SAF.

### 10.6 Efficacy Results

#### 10.6.1 Primary Efficacy Analysis

Table **CCI** summarizes change from baseline in the average minutes of MVPA at day 7, day 14 and day 21 by summary statistics by timepoint along with the analysis results specified in section 8.2.2 for the mITT.

Figure **CCI** presents MVPA over time for the mITT.

Listing **CCI** presents all MVPA data for the mITT.

#### 10.6.2 Secondary Efficacy Analysis

Change from baseline at day 7, day 14 and day 21 tables are summarized by summary statistics by timepoint along with the analysis results specified in section 8.2.3 for the mITT, for each of the following secondary endpoints:

- Daily Average number of steps taken in Table **CCI**
- Ratio of sedentary/non-sedentary time in Table **CCI**
- Gait, assessed through speed and step irregularity in Table **CCI**
- Indices of morning stiffness in Table **CCI**
- WOMAC scores including Pain, Stiffness and Physical function subscales in Table **CCI**
- NRS in in Table **CCI**

Change from baseline at day 7, day 14 and day 21 tables are summarized by summary statistics by timepoint for the mITT, for each of the following secondary endpoints:

- MVPA on each day of the study in Table **CCI**
- Karolinska Sleepiness Scale in Table **CCI**
- EQ-5D-5L Index in Table **CCI**

Table **CCI** summarizes EQ-5D-5L response data over time by treatment and overall.

Listings CCI [REDACTED] present all data for each of the endpoints for the mITT.

Figures CCI [REDACTED] presents over time graphs for each of the endpoints for the mITT.

Figure CCI [REDACTED] presents the correlation between WOMAC scores and MVPA for the mITT.

### 10.6.3 Exploratory Analysis

A Kaplan-Meier analysis is performed on the time to meaningful pain relief data on the mITT population as described in section 8.2.4. Table CCI [REDACTED] summarizes the number of patients with event, the number patients with censoring, the median time to meaningful pain relief with its 95% CI as well as Q1 and Q3.

Listing CCI [REDACTED] presents the time to meaningful pain relief data for the mITT.

Figure CCI [REDACTED] presents the Kaplan-Meier graph for the mITT.

## 10.7 Safety Results

### 10.7.1 Adverse Events

#### 10.7.1.1 Brief Summary of Adverse Events

An Overview of AEs including but not limited to

- the number of subjects with at least one AE;
- the number of subjects with at least one pre-treatment AE;
- the number of subjects with at least one TEAE;
- the number of subjects with at least one Serious TEAE;
- the number of subjects who permanently discontinued Study Treatment due to a TEAE;
- the number of subjects with a TEAE related to study treatment;
- the number of subjects who had a TEAE with outcome of death
- the worst severity of any TEAE experienced by each subject with at least one TEAE

is summarized by treatment and overall, for the SAF in Table CCI [REDACTED]

#### 10.7.1.2 Display of Adverse Events

Adverse event descriptive tables are summarized on a per-subject basis (i.e. if a subject reported the same event repeatedly the subject is counted only once at the specific level of display) and on a per event basis. Absolute counts (n) and percentages (%) are presented for the number of subjects with at least one adverse event, and per SOC and per PT within SOC, by treatment and overall, for the SAF. Percentages are based on the number of subjects in the population. Descriptive tables are sorted alphabetically by SOC and by PT within SOC.

Descriptive tables are ordered by descending frequency of the overall number of subjects within each SOC, and then ordered within each SOC by the overall number of subjects within each PT. In the event of equal frequencies tables are ordered alphabetically.

TEAEs are summarized for the SAF, as follows:

- TEAEs in Table CCI [REDACTED]
- Serious TEAEs in Table CCI [REDACTED]
- Related TEAEs in Table CCI [REDACTED]

#### 10.7.1.3 Listing of Adverse Events

Listing **CCI** presents all Adverse Event data (raw, derived, and coded), for the SAF.

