## Footnotes:

a Actigraph tracker is dispensed at screening visit post consent of patient during enrolment for the study (D -7 – Visit 1). and Voltaren is dispensed immediately post eligibility of the subject at the end of Baseline period (Day 0 – Visit 2).

b The questionnaires such as: Pain Visual Analogue Scale (VAS) / Numeric Rating Scale (NRS), will initially be performed on site during enrolment period (Visit 1) and prior to dispensing of Voltaren (Visit 2), to complete the baseline assessment. Subjects are then required to perform the assessment of NRS, Western Ontario and McMaster University Osteoarthritis index (WOMAC), Karolinska Sleepiness Scale and the EQ-5D-5L Health questionnaire at site prior to dispensing of Voltaren (Day 0 – Visit 2) and then at home during the study period and report the score within the eDiary.

c Adverse Events (AEs) and therefore all Serious Adverse Events (SAEs) will be collected immediately after a subject provides consent to participate in the study by the completion of the Informed Consent Form (ICF).

\* Baseline period will be flexible and last a minimum of 3 days and maximum 7 days to collect sufficient baseline information from study subjects. When pain levels reach  $\geq 40$  mm  $\leq 70$ mm in the VAS/NRS scale, the day before starting the use of Voltaren, study subjects will be prompted to answer relevant questionnaires to assess baseline levels. Site staff to monitor subjects eDiary and dispense Voltaren when patients have ended baseline period. Subjects can also notify site staff when their baseline period has ended to commence the study.

\*\* Study period will last a maximum of 28 days. Study subjects are allowed to stop using Voltaren if they feel that their pain has successfully resolved and do not need to use the product anymore.

\*\*\*Urine test only needed for women of childbearing potential and postmenopausal women who are not surgically sterile. Urine samples are collected to detect the presence of human chorionic gonadotropin (hCG), a hormone produced during pregnancy.

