### 11.3 Reporting Procedures

The investigator is responsible for detecting, documenting, and reporting events that meet the definition of an AE and remain responsible for following up on AEs that are serious, considered related to the study product(s), participation in the study, or a study procedure, or that caused the subject to discontinue the study product or study.

Each AE is to be assessed to determine if it meets the criteria for a SAE. If an SAE occurs, expedited reporting will follow local and international regulations, as appropriate.

When an AE occurs, it is the responsibility of the investigator (or medically qualified designee) to review all documentation (e.g., hospital progress notes, laboratory, and diagnostics reports) related to the event.

The investigator or site staff will then record all relevant information regarding an AE in the eCRF and all details relating to an SAE in the paper SAE Form provided.

It is **not** acceptable for the investigator (or medically qualified designee) to send photocopies of the subject's medical records to Haleon in lieu of completion of the AE eCRF page/SAE form.

The investigator (or medically qualified designee) will attempt to establish a diagnosis of the event based on signs, symptoms, and/or other clinical information. The diagnosis will be the documented as the AE/SAE where known and not the individual signs/symptoms. (e.g., upper respiratory tract infection, seasonal allergy, etc. instead of runny nose).

AEs elicited by the investigator (or medically qualified designee) in a standard manner at the study visits should also be recorded in the AE section of the eCRF and/or using the SAE form (subject to the classification of the AE). Care will be taken not to introduce bias when questioning a subject about any changes in their health. Open-ended and non-leading verbal questioning should be used.

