**Table 11-2 Adverse Reaction Frequency**

MedDRA SOC	Adverse Reaction	Frequency
Infection and infestation	Rash pustular	Very rare
Immune system disorders	Angioedema, hypersensitivity (including urticaria)	Very rare
Respiratory, thoracic and mediastinal disorders	Asthma	Very rare
Skin and subcutaneous tissue disorders	Dermatitis (including contact dermatitis), rash, erythema, eczema, pruritus.	Common
	Dermatitis bullous	Rare
	Photosensitivity reaction	Very rare

Overdosage:

The low systemic absorption of topical diclofenac renders overdose unlikely. However undesirable effects, similar to those observed following an overdose of diclofenac tablets, can be expected if topical diclofenac is ingested. In the event of accidental ingestion, resulting in significant systemic adverse effects, general therapeutic measures normally adopted to treat poisoning with non-steroidal anti-inflammatory medicines should be used.

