### **13.3.3 Safety Analysis(es)**

All AEs will be coded using MedDRA. AEs will be categorized as related, probable, unlikely, or unrelated by responsible authority prior to database lock. The number of AEs/SAEs and number of subjects with AEs/SAEs will be listed and tabulated.

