## 7.4.8 Safety Variables

### Adverse Events

An adverse event (AE) is defined as “any untoward medical occurrence in a clinical study subject, temporally associated with the use of a study product including any washout or lead-in product (or medical device), whether or not considered related to the study product, including any washout or lead-in product (or medical device)”.

An AE can therefore be any unfavourable and unintended sign (including an abnormal laboratory finding), symptom, or disease (new or exacerbated) temporally associated with the use of a study product including any washout or lead-in product (or medical device).

AE data are collected from the time that informed consent was given for the duration of the trial on the ‘Adverse Events’ eCRF page.

The following information is recorded:

- AE term;
- Start date/time;
- End date/time (or ongoing);
- Severity (“Mild”, “Moderate”, or “Severe”);
- Serious (“Yes”, “No”)
  - if AE is serious:
    - Death (‘No’, ‘Yes’) if yes then also date of death;
    - Life threatening (‘No’, ‘Yes’);
    - Hospitalization (‘No’, ‘Yes’) if yes then also start and end date;
    - Significant Disability (‘No’, ‘Yes’);
    - Congenital Anomaly or Birth Defect (‘No’, ‘Yes’);
    - Other Medically important event (‘No’, ‘Yes’);
- Outcome (“Fatal”, “Not recovered/ not resolved”, “Recovered/ resolved”, “Recovered with sequelae / resolved with sequelae”, “Recovering / resolving”, or “Unknown”);
- Relationship to study drug (“Unknown”, “Not Related”, “Unlikely”, “Possible”, “Probable”, or “Definite”);
- Action taken with study treatment (“Dose not changed”, “Dose increased”, “Dose rate reduced”, “Dose reduced”, “Drug interrupted”, “Drug withdrawn”, “Not applicable”, or “Unknown”);
- Other action taken:
  - None (‘No’, ‘Yes’);
  - Medication prescribed (‘No’, ‘Yes’);
  - Device removed (‘No’, ‘Yes’);
  - Surgery (‘No’, ‘Yes’);
  - Other (‘No’, ‘Yes’);

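### AEs are collected from consent, but every AE output is limited to gel users, so AEs in subjects who never enter the safety population are reported nowhere as AEs

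*SAP*

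**What the plan says.** Protocol 1.1 (Schedule of Activities, footnote c) says that AEs and SAEs "will be collected immediately after a subject provides consent to participate in the study". Footnote a says "Actigraph tracker is dispensed at screening visit post consent of patient during enrolment for the study". The gel follows at Day 0, after a baseline period of 3 to 7 days (Protocol 9.2.1). The protocol's AE definition (11.1) covers medical devices.

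Protocol 13.3.3 promises: "The number of AEs/SAEs and number of subjects with AEs/SAEs will be listed and tabulated". It names no population there; Protocol 13.2 assigns the safety population to safety variables.

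SAP 6.1 puts a subject in the SAF if there is a date of first study treatment administration. SAP 7.1 derives that date from the first diary Yes to having used the gel according to its label. In SAP 10.7.1 the overview, which includes "the number of subjects with at least one pre-treatment AE", is on the SAF. So are the system organ class and preferred term tables, and the listing "presents all Adverse Event data (raw, derived, and coded), for the SAF".

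On causality, the AE eCRF page in SAP 7.4.8 has the item "Relationship to study drug" and no device item, although removal of the device is one of the recorded actions. SAP 7.4.8 counts Unlikely and Unknown as related to treatment.

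**The concern.** The safety objective concerns AEs over the study period, and the SAP shows by its pre-treatment row that it means to report the time before first gel use. Restricting that row to gel users selects on the outcome: a subject whose baseline AE led to withdrawal before first use is left out of the count of baseline AEs. The listing is described as showing all AE data but omits AEs that were collected under the protocol. For an SAE in such a subject, a reader of the study report would find no term, severity, seriousness criterion or outcome in the AE outputs.

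A smaller question concerns the wrist device. The gel's only reactions classed as common in Protocol Table 11-2 are "Dermatitis (including contact dermatitis), rash, erythema, eczema, pruritus", and a strap could cause similar complaints. Protocol 11.3 asks for follow-up of events "considered related to the study product(s), participation in the study, or a study procedure", but the AE eCRF page attributes causality to the drug alone, and no planned output identifies events at the device site.

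**Working it through.** **1. Which outputs a subject reaches.** Apply SAP 6.1, 7.1, 7.4.8, 10.1 and 10.7.1 to three kinds of subject.

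- *AE in baseline, then starts the gel.* In the SAF. Counted in the pre-treatment row and shown in the listing. Absent from the term-level tables named in SAP 10.7.1.2, which cover TEAEs only.
- *AE in baseline, withdraws before first use.* Not in the SAF, so in neither the overview, the tables nor the AE listing. If the AE is the primary reason for leaving, the Study Termination page records the AE number (SAP 7.4.1), and the disposition listing, on the Total Set, shows the reason. If the AE is not the primary reason, nothing appears.
- *Uses the gel but never records a diary Yes.* No first-treatment date can be derived, so the subject is outside the SAF and AEs during actual use also go unlisted. The diary asks about use as labelled, so a No need not mean no use.

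**2. How many subjects.** The plan's figures first: 195 × (1 − 0.25) = 146.25 and 147 / 0.75 = 196, so 195 enrolled and 147 completers agree to within one subject.

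Expected non-completers: 195 − 147 = 48, or 48 / 195 = 24.6%.

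Let m be the enrolled subjects who never use the gel. The documents do not give m. Protocol 9.2.2 treats them as dropouts, so under the planned dropout 0 ≤ m ≤ 48. Let p be the proportion of them with an AE, also not given. Subjects with an AE and no AE output = m × p. With p = 10%, chosen only for illustration:

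| m (assumed) | share of 195 | m × 10% |
|---|---|---|
| 0 | 0% | 0 |
| 5 | 2.6% | 0.5 |
| 10 | 5.1% | 1 |
| 20 | 10.3% | 2 |
| 48 | 24.6% | 4.8 |

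The last row is extreme, since most dropouts would be expected to have used the gel first. Against that, p = 100% among those who leave because of an AE, so 10% may be too low for early leavers. Consented screen failures, and gel users without a diary Yes, come on top and cannot be counted from the documents.

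**3. Direction.** Subjects with a pre-treatment AE = those in the SAF + those outside it. The planned row shows only the first term, so it can equal or understate the total but never overstate it. No pre-treatment SAE row is named for either group.

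**4. A strap reaction under SAP 7.4.8.**

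- Onset before first gel use: a pre-treatment AE, so in no TEAE table.
- Onset on or after first use, rated Not Related: in the TEAE table, not in the Related TEAE table.
- Onset on or after first use, rated Unlikely, Possible, Probable, Definite or Unknown: in the Related TEAE table. An investigator who suspects the strap but is not certain, and so chooses Unlikely, thereby adds a gel-related event.

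**The case against.** The SAF restriction follows the protocol. Section 13.2 defines the safety population as product users and assigns it to safety variables, and the safety endpoint in Table 3-1 concerns events on treatment. Subjects outside the SAF are not invisible: the Total Set disposition listing carries the discontinuation reason, and SAEs from consent onward reach the sponsor within 24 hours whatever the analysis set (Protocol 11.3.2). The overview is not limited to the rows named, and exact specifications sit in a separate shell document, so a pre-treatment SAE row may exist there.

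This stands as far as the TEAE tables go, and they should stay on the SAF. It does not justify a listing of all AE data that leaves out collected AEs, or a pre-treatment row that excludes those who left during that period. Expedited reporting is not study reporting. The SAP already uses the Total Set for screen failures, disposition, eligibility and VAS (10.1, 10.2.1, 10.4.4).

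Three stronger readings might be inferred, and the documents do not support them.

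- *All harm before first use is lost.* No: gel users' pre-treatment AEs are counted and listed.
- *Causality is recorded against the drug only.* This holds for the AE eCRF page, but the SAE form allows relationship to a study procedure (Protocol 11.3.2). Protocol 11.3 concerns follow-up and does not require a device item.
- *The gel's skin reaction rate necessarily contains strap reactions.* No: a wrist reaction can be rated Not Related, and those starting before first gel use are not TEAEs. That strap and gel rashes code to the same preferred terms is plausible but not documented.

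**Conclusion.** The reporting gap is real but narrow. AEs and SAEs in consented or enrolled subjects who never enter the SAF are collected and then have no AE output, and the pre-treatment count omits subjects whose baseline AE led them to withdraw before first use. The size is not known. Enrolled non-users are bounded only by 0 to 48 of 195, which rests on the planned dropout being realised and on non-users being counted as dropouts. Only those with an AE matter, so the number is probably small. A single SAE in this group would still be enough to make the listing materially incomplete.

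Mixing of device and gel reactions in the Related TEAE table is a possibility created by the Unlikely and Unknown rule, not a demonstrated error. No figure for it can be taken from the documents.

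**What to change.** **Main change.** In SAP 10.7.1.3, produce the AE listing for the Total Set with an SAF flag. In SAP 10.7.1.1, produce the pre-treatment AE row for the Total Set, state its denominator, and add a pre-treatment SAE row. Keep all TEAE tables and TEAE rows on the SAF. Cost: a population flag on one listing and two overview rows. Because the SAP labels subjects by the gel assigned at baseline (7.3), anyone who leaves before assignment needs a column for no gel assigned or appears under overall only. No new data, visits or assessments are needed.

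**Secondary addition.** Flag each skin TEAE as gel site, device site or other, from the verbatim term and the device-removal field, and show the flag in the listing and beside the Related TEAE table. SAP version 2.0 already incorporates updates from the data review meeting, so this should be a separate documented step before database lock. Cost: a short classification exercise, which may be incomplete where the verbatim term gives no body site. It needs no new eCRF item.
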